#### 7.4.1.3 **Definition of the Adverse Event Reporting Period**

The AE reporting period for safety surveillance will begin when the subject is initially included in the trial (date of first signature of informed consent) and continue through the 90-Day Safety Follow-up Phone Call, which is defined as occurring 90 days ( $\pm$  5 days) after last study drug administration.

Any SAE assessed as related to IMP must be reported whenever it occurs, irrespective of the time elapsed since the last administration of IMP.

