For reporting conventions, mean and median should generally be displayed one more decimal place than the raw data and standard deviation should be displayed to two more decimal places than the raw data. Percentages will be reported to one decimal place. The rounding will be performed to closest integer / first decimal using the common mid-point between the two

consecutive values. E.g. 6.1 to 6.4 will be rounded to an integer of 6, and 6.5 to 6.9 will be rounded to an integer of 7.

Unscheduled visits:

Generally, data collected at unscheduled visits will be included and analyzed for both safety and efficacy analyses in the same fashion as the data collected at scheduled visits except where otherwise noted in the sections that follow. Descriptive statistics (mean, SD, median, minimum, maximum, quartiles) by nominal visit or time point for safety endpoints such as laboratory measurements, ECGs and vital signs will include only data from scheduled visits.

Handling of missing data and imputation rules:

Unless otherwise specified, all data will be evaluated as observed, and no imputation method for missing values will be used.

In all subject data listings imputed values will be presented. In all listings imputed information will be flagged.

Missing statistics, e.g. when they cannot be calculated, should be presented as 'ND' or 'NA'. For example, if N=1, the measure of variability (SD) cannot be computed and should be presented as 'ND'.

Disease history:

Incomplete dates for disease history (e.g. initial diagnosis date, date of documented, metastatic disease diagnosis, date of response or progression in prior treatment) will be imputed as follows:

- If the day is missing, it will be imputed to the 15th day of the month.
- If both day and month are missing and the year is prior to the year of the first study treatment, the month and day will be imputed as July 1st.
- If both day and month are missing and the year is same as the year of the first study treatment, the month and day will be imputed as January 1st.
- If the date is completely missing, no imputation will be performed.
- For all imputed disease history dates, the imputed date will be set equal to the maximum of the imputed date as specified above and the subject's date of birth.

Adverse events:

Incomplete AE-related dates will be imputed as follows:

- If the AE onset date is missing completely, then the onset date will be replaced by the start of study treatment.

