- If only the day part of the AE onset date is missing, but the month and year are equal to the start of study treatment, then the AE onset date will be replaced by the start of study

treatment. For example, if the AE onset date is --/JAN/2015, and study treatment start date is 15/JAN/2015, then the imputed AE onset date will be 15/JAN/2015.

- If both the day and month of the AE onset date are missing but the onset year is equal to the start of study treatment, then the onset date will be replaced by the start of study treatment. For example, if AE onset date is --/--/2014, and study treatment start date is 19/NOV/2014, then the imputed AE onset date will be 19/NOV/2014.
- In all other cases the missing onset day or missing onset month will be replaced by 1.
- For all imputed AE start dates, the imputed date will be set equal to the maximum of the imputed date as specified above and the subject's date of birth.
- Incomplete stop date will be replaced by the last day of the month (if day is missing only), if not resulting in a date later than the date of subject's death. In the latter case the date of death will be used to impute the incomplete stop date.
- In all other cases the incomplete stop date will not be imputed. If stop date of AE is after date of cut-off outcome of AE is ongoing at cut-off.

Prior and concomitant medications:

Incomplete prior/concomitant medication start dates will be imputed as follows:

- If the medication start date is missing completely, then the medication start date will be replaced by the start of study treatment.
- If the day of medication date is missing, but the month and year are equal to the start of study treatment, then the medication start date will be replaced by the start of study treatment. For example, if the medication start date is --/JAN/2015, and study treatment start date is 15/JAN/2015, then the imputed medication start date will be 15/JAN/2015.
- If both the day and month of medication start date are missing but the start year is equal to the start of study treatment, then the medication start date will be replaced by the start of study treatment. For example, if the medication start date is --/--/2014, and study treatment start date is 19/NOV/2014, then the imputed medication start date will be 19/NOV/2014.
- In all other cases the missing medication day or missing medication month will be replaced by 1.

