- For all imputed prior/concomitant start dates, the imputed date will be set equal to the maximum of the imputed date as specified above and the subject's date of birth.
- Incomplete stop date will be replaced by the last day of the month (if day is missing only), if not resulting in a date later than the date of subject's death. In the latter case the date of death will be used to impute the incomplete stop date.
- In all other cases the incomplete medication stop date will not be imputed.

In case an imputed medication start date is later than the medication stop date, it will be replaced by the medication stop date.

Subsequent anti-cancer therapy

Incomplete subsequent anti-cancer therapy start dates will be imputed as follows:

- If only day is missing, it will be imputed as the last day of the month unless the end date of subsequent anti-cancer therapy is before that date. In that case, the incomplete anti-cancer therapy start date will be imputed as the end date of the anti-cancer therapy.
- If both day and month are missing, no imputation will be performed.

Exposure:

- In case the study drug start date is missing, no imputation will be performed.
- In case the last date of study drug is incomplete the date of last administration of study drug will be taken from the treatment termination eCRF pages.

Date of last contact:

The date of last contact will be derived for subjects not known to have died at the analysis cut-off using the latest complete date among the following:

- All subject assessment dates (blood draws (laboratory, PK), vital signs, performance status, ECG, tumor assessments)
- Start and end dates of anti-cancer therapies administered after study treatment discontinuation.
- AE start and end dates
- Date last known to be alive collected on the eCRF form "Subject Status / Survival Follow-up" Study drug start and end dates
- Date of discontinuation on disposition eCRF pages (do not use if reason for discontinuation is lost to follow-up).

Only dates associated with actual examinations of the subject will be used in the derivation. Dates associated with a technical operation unrelated to subject status such as the date a blood sample was processed will not be used. Assessment dates after the cut-off date will not be applied to derive the last contact date.

Death Date:

Missing or partial death dates will be imputed based on the last contact date:

- If the date is missing it will be imputed as day after date of last contact

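### Three AE onset imputation rules set the date to first dose without checking the stop date, so an AE recorded as ending before treatment can count as treatment-emergent

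*SAP*

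**What the plan says.** SAP Section 9 (handling of missing data, adverse events) moves an incomplete AE onset to the date of first dose in three cases:

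- Onset fully missing: "If the AE onset date is missing completely, then the onset date will be replaced by the start of study treatment".
- Day missing, in the month and year of first dose, a rule that opens "If only the day part of the AE onset date is missing, but the month and year are equal to the start".
- Day and month missing, in the year of first dose, a rule that opens "If both the day and month of the AE onset date are missing but the onset year is equal to the start of study treatment".

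Other partial onsets are not moved to first dose: "In all other cases the missing onset day or missing onset month will be replaced by 1". One bound follows, with date of birth as the other term: "For all imputed AE start dates, the imputed date will be set equal to the maximum of the imputed date as specified above". That is a floor. The AE stop-date rules fill a missing day with the month end, limited by the date of death, and do not refer to onset or to first dose.

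The medication rules in the same section repeat the same three cases and then add: "In case an imputed medication start date is later than the medication stop date, it will be replaced by the medication stop date". The subsequent anti-cancer therapy rule likewise uses the end date when it is earlier than the imputed start.

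SAP Section 9 starts the on-treatment period at first dose. SAP Section 15.2 defines a TEAE by onset (or worsening) in that period, without a condition on the stop date, and names Grade 3 or higher TEAEs as a primary endpoint.

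**The concern.** Setting an unknown onset to first dose is a common conservative rule, and acceptable when nothing else is known about the timing. It stops being reasonable when the same record carries a stop date before first dose. The event is then known to have ended before any avelumab was given, yet the rule gives it an onset on Day 1.

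Because treatment-emergence is judged on onset, that record becomes a TEAE. At Grade 3 or higher it counts in the primary endpoint table (SAP Section 15.2.1) and in the Grade 3 or higher TEAE row for the DLT evaluation period (SAP Section 15.1); SAP Section 6 lists the corresponding DLT-period TEAE output among what the SMC reviews. At lower grades it affects the secondary TEAE tables. The presence of the check in the two neighbouring sets of start-date rules suggests an omission rather than a choice.

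**Working it through.** **1. The SAP's own examples.** Applying the rules as written to the two worked cases in SAP Section 9:

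- Onset --/JAN/2015, first dose 15/JAN/2015: imputed onset 15/JAN/2015.
- Onset --/--/2014, first dose 19/NOV/2014: imputed onset 19/NOV/2014.

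Both agree with the SAP.

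**2. Adding a stop date.** The stop dates and incomplete onsets below are assumed for illustration, with first dose on 15 January 2015 as in the SAP's first example. Duration follows SAP Section 9: stop minus start plus 1. The capped onset is the earlier of the imputed onset and the stop date.

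| Recorded onset | Stop | Imputed onset | Duration (days) | TEAE as written | Capped onset | TEAE with cap |
|---|---|---|---|---|---|---|
| fully missing | 8 Jan 2015 | 15 Jan 2015 | 8 − 15 + 1 = −6 | yes | 8 Jan 2015 | no |
| --/JAN/2015 | 10 Jan 2015 | 15 Jan 2015 | 10 − 15 + 1 = −4 | yes | 10 Jan 2015 | no |
| --/--/2015 | 10 Jan 2015 | 15 Jan 2015 | 10 − 15 + 1 = −4 | yes | 10 Jan 2015 | no |
| --/DEC/2014 | 10 Jan 2015 | 1 Dec 2014 | 41 | no | unchanged | no |
| --/--/2014 | 10 Jan 2015 | 1 Jan 2014 | 375 | no | unchanged | no |

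The three first-dose cases each produce a TEAE with negative duration, and the cap corrects each. The last two rows show that other partial onsets are not affected.

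**3. Whether AEs before first dose are in the data.** The protocol is not consistent.

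- Section 7.4.1.3: the AE reporting period "will begin when the subject is initially included in the trial (date of first signature of informed consent"). Section 7.4 assesses toxicity from consent, and Section 7.4.4 has conditions seen from Screening reported as AEs. Section 7.1.1 allows up to 28 days for Screening.
- Table 1, footnote k: serious and non-serious AEs go on the eCRF once at least one dose has been taken, while SAE reporting runs from consent.
- SAP Section 15.2 lists AEs whether or not they are treatment-emergent, but that also covers events after treatment.

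**4. Size per affected subject.** The tables count subjects, so one misclassified subject changes a proportion by at most 1/n. The protocol requires at least 12 DLT-evaluable subjects and plans 12 to 36 in Phase I (Section 5.1.1). The intervals are exact Clopper-Pearson 95%, the method SAP Section 15.1 names for the DLT-period rows.

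- n=12: 1/12 = 8.3 points. 0/12 gives 0 to 26.5%; 1/12 gives 0.2 to 38.5%.
- n=36: 1/36 = 2.8 points. 0/36 gives 0 to 9.7%; 1/36 gives 0.1 to 14.5%.

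The change is zero if the subject already has a genuine Grade 3 or higher TEAE in the same period.

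**The case against.** The strongest reply is that the affected set is very small. To reach the primary endpoint, a record must be an AE rather than an unchanged baseline condition (Protocol Section 7.4.1.1), be Grade 3 or higher, fall under one of the three first-dose rules, and carry a stop date before first dose. On footnote k, non-serious events before first dose would not be on the eCRF at all. AE reports are meant to include onset and resolution dates (Protocol Section 7.4.1.2), queries are resolved before lock (SAP Section 6), and imputed values are flagged in listings (SAP Section 9), so an onset later than its stop would be visible. The error can only over-count toxicity, and the analysis is descriptive.

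Most of this stands as a limit on frequency and size. It does not close the gap. Flags and queries make a case visible, but no SAP rule then removes it from the tables. Erring towards over-counting is a reason for the rule when timing is unknown, not when the stop date settles it.

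A reader might infer four stronger things that the documents do not support:

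- **That every partial onset moves to first dose.** Only the three listed cases do.
- **That AEs before first dose are certainly in the database.** Footnote k conflicts with Sections 7.4, 7.4.1.3 and 7.4.4, although SAE reporting from consent keeps some exposure on either reading.
- **That each such subject adds 8.3 points.** That is a maximum at n=12.
- **That dose decisions are affected.** DLTs are a separate recorded item analysed per SMC assessment (SAP Section 15.1), and the mTPI scheme uses DLT counts. An imputed TEAE date creates no DLT.

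**Conclusion.** The point holds as a defect in a written rule. In three defined cases SAP Section 9 assigns an onset later than a known stop date, and the TEAE definition then counts the event as treatment-emergent. No other AE rule in the SAP corrects it.

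The practical effect is probably small. The documents give no count of incomplete onset dates, so the frequency is unknown. The per-subject maxima above assume that an event before first dose was recorded as an AE, was Grade 3 or higher, had an incomplete onset of one of the three kinds, and occurred in a subject with no genuine Grade 3 or higher TEAE in the period. The correction is warranted because the result is wrong whenever the case arises and the remedy is already in use a few lines further on.

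**What to change.** Add two sentences to the AE rules in SAP Section 9, for example: *An imputed AE onset that falls after the AE stop date (recorded, or as imputed) is set to the AE stop date. An AE with a stop date earlier than first dose is not treatment-emergent.*

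This leaves the conservative default in place wherever the stop date is missing, or falls on or after first dose. A stop date with only the day missing is imputed to month end (or to the date of death if earlier), so a stop in the first-dose month normally stays on or after first dose and the event remains a TEAE.

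Separately, reconcile Table 1 footnote k with Protocol Sections 7.4, 7.4.1.3 and 7.4.4, or state in the SAP which start of AE recording the database follows, so that the exposure is known.

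The cost is two sentences of text and about one line of derivation code. No further data collection is needed for the cap.

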10.1 Disposition of Subjects and Discontinuations

The following will be summarized overall and by dose level.

The percentages below will be calculated based on the number of subjects in the FAS.

- Total number of subjects screened
- Number of subjects who screen failed prior to enrollment overall and by reason for screen failure
- Number and percentage of treated subjects in the following populations:
 - FAS
 - Safety analysis set

- DLT analysis set
- Immunogenicity analysis set
- PK analysis set
- Biomarker analysis set
- Number of treated subjects
- Number of subjects that received no treatment
- Number and percentage of subjects still on treatment
- Number and percentage of subjects who discontinued treatment overall and per reason of treatment discontinuation
- Number and percentage of subjects who discontinued the treatment but are still in follow-up
- Number and percentage of subjects who re-initiated avelumab treatment and discontinued treatment after re-initiation
- Number and percentage of subjects who discontinued the trial overall and by the main reason for discontinuation

10.2 Protocol Deviations

10.2.1 Important Protocol Deviations (IPDs)

Important protocol deviations (IPDs) are protocol deviations that might significantly affect the completeness, accuracy, and/or reliability of the study data or that might significantly affect a participant's rights, safety, or well-being.

Important protocol deviations include:

- Participants enrolled and dosed on the study who did not satisfy enrolment criteria
- Participants that develop withdrawal criteria whilst on the study but are not withdrawn
- Participants that receive the wrong study intervention or an incorrect dose
- Participants that receive an excluded concomitant medication
- Failure to collect data necessary to interpret primary endpoints
- Failure to collect necessary key safety data
- Deviation from Good Clinical Practice (GCP)
- Any other protocol deviation that might significantly affect the completeness, accuracy, and/or reliability of the study data or that might significantly affect a participant's rights, safety, or well-being.

Important protocol deviations will be identified for all participants by either site monitoring, medical review processes or programming and confirmed prior to or at the Data Review Meeting at the latest.

All important protocol deviations are captured in SDTM datasets, whether identified through site monitoring, medical review or programming. The management of protocol deviations is outside of this IAP document.

IPDs will be listed for all subjects in the FAS.

IPDs will be determined for all subjects by either medical review processes or programming based on the inclusion/exclusion criteria or other criteria presented in the protocol.

The complete list of IPDs is maintained by the medical team in the Clinical Trial Management System (CTMS) and will be finalized prior to database lock.

10.2.2 Protocol Deviations Related to the COVID-19 Pandemic

Protocol deviations that are identified as being caused by the impact of the COVID-19 pandemic, such as those resulting from illness, changes in local regulations, or changes by subject behavior, will be documented in CTMS and flagged accordingly by site monitors. All COVID-19 related protocol deviations are captured in SDTM datasets, regardless of whether the deviation is classified as “Important” or “Minor”.

A listing of protocol deviations related to the COVID-19 pandemic will be prepared. The listing will include all such protocol deviations reported, including non-important deviations.

11 Demographics and Other Baseline Characteristics

If not stated otherwise, summaries will be presented for the FAS by dose level and overall.

11.1 Demographics

Demographic characteristics and physical measurements will be summarized using the following information from the ‘Demographics’ eCRF page.

- Demographic characteristics
 - Sex: Male, Female
 - Race: White, Black or African American, Asian, American Indian or Alaska Native, Native Hawaiian or other Pacific Islander, Other, Not collected at this site
 - Ethnic origin: Hispanic or Latino (Yes/No), Japanese (Yes/No)
 - Age (years)

-
- Age categories :
 - < 1 year
 - 1 - 12 years
 - > 12 years
 - Geographic Region (as applicable):
 - North America
 - Latin America
 - Western Europe
 - Eastern Europe
 - Middle East
 - Australasia
 - Asia
 - Africa
 - European Economic Area (EEA): Yes or No
 - Lansky Performance Status
 - Karnofsky Performance Status
 - Physical measurements
 - Height (cm)
 - Weight (kg)
 - Body Mass Index (BMI) (kg/m²)
 - Body Surface Area (BSA) (m²)

Site codes will be used for the determination of the subject's geographic region.

The listing of demographics and baseline characteristics will include the following information: subject identifier, dose level, age, sex, race, ethnicity, height (cm), weight (kg), gestational age, BMI (kg/m²), BSA (m²), Karnofsky and Lansky performance status.

11.2 Medical History

Medical history will be coded using the most current available version of Medical Dictionary for Regulatory Activities (MedDRA) and will be summarized from the "Medical History" eCRF page. Medical history details for subjects in the Full Analysis Set will be provided in a listing.

11.3 Disease Characteristics

Information on disease characteristics collected on the "Disease History" eCRF page and the "Cohort" eCRF page will be summarized along with tumor category (see Section 8.2) and PD-L1 expression status as assessed by a central lab. Summary statistics will be presented for:

-
- PD-L1 expression status (positive/negative) at cut-offs 1%, 5%, 25%, 50%, 80%
 - Type of primary tumor (solid tumor/lymphoma) Tumor category (soft tissue/bone sarcoma, GI, CNS)
 - Time since initial cancer diagnosis (months), defined as (start date of study treatment – date of initial cancer diagnosis)/30.4375
 - Time since metastatic disease (months), defined as (start date of study treatment – date of metastatic disease)/30.4375
 - Stage at initial diagnosis
 - TNM classification at initial diagnosis
 - Stage at study entry
 - TNM classification at study entry

A listing of disease history will be provided with all relevant data (as collected on the “Disease History” and “Cohort” eCRF pages) and derived variables used in the above table.

11.4 Prior Anti-Cancer Therapies

The prior anti-cancer therapies are collected under the “Prior Anti-Cancer Drug Therapies Details”, “Prior Anti-Cancer Radiotherapy Details” and “Prior Anti-Cancer Surgeries Details” eCRF pages.

The number and percentage of subjects in each of the following anti-cancer therapy categories will be tabulated:

- Subjects with at least one type of prior anti-cancer treatment
- Subjects with at least one prior anti-cancer drug therapy
- Subjects with at least one prior anti-cancer radiotherapy
- Subjects with at least one prior anti-cancer surgery

Prior anti-cancer drug therapy will be summarized as follows:

- Number and percentage of subjects with at least one prior anti-cancer drug therapy
- Number and percentage of subjects with number of any prior anti-cancer therapy regimens: missing / 1 / 2 / 3 / ≥ 4
- Number and percentage of subjects with number of prior anti-cancer therapy regimens for metastatic disease: missing / 1 / 2 / 3 / ≥ 4
- Type of prior anti-cancer therapy: Cytotoxic / Endocrine / Monoclonal Antibodies / Targeted / Immunotherapy / Other
- Intent of Therapy: Metastatic / Non metastatic

- Best response: Complete Response (CR) / Partial Response (PR) / Stable Disease (SD) / Non-complete Response/Non-Progressive Disease (Non-CR /Non-PD) / Progressive Disease (PD) / Not Evaluable / Unknown.

Best response is derived from the last treatment regimen.

The prior anti-cancer drugs will also be summarized based on the number and percentage of subjects by the drug class and preferred term within each regimen number. A subject will be counted only once within a given drug class and within a given drug name, even if he/she received the same medication at different times. The summary will be sorted on decreasing frequency of drug class and decreasing frequency of drug name in a given drug class. In case of equal frequency regarding drug class (respectively drug name), alphabetical order will be used.

A listing of prior anti-cancer treatments and procedures will also be provided. This listing will include the subject identification number, and all the relevant collected data-fields on the corresponding eCRF pages:

- Prior anti-cancer drug therapies
- Prior anti-cancer radiotherapy
- Prior anti-cancer surgeries

12 Prior or Concomitant Medications/Procedures

Concomitant medications are medications, other than study medications, which started prior to first dose date of study treatment and continued into the on-treatment period as well as those started during the on-treatment period. **Prior medications** are medications, other than study medications and pre-medications for study drug, which are started before first dose date of study treatment.

Concomitant medications will be summarized from the “Concomitant Medications Details” eCRF page.

In cases where the date values do not allow unequivocal allocation of a medication to concomitant (as opposed to prior) medication the medication will be considered as concomitant medication.

Summary of concomitant medications will include the number and percentage of subjects by Anatomical Therapeutic Chemical (ATC) Classification level 2 and preferred term. A subject will be counted only once within a given drug class and within a given drug name, even if he/she received the same medication at different times. If any concomitant medication is classified into multiple ATC classes, the medication will be summarized separately under each of these ATC classes. The summary tables will be sorted on decreasing frequency of drug class and decreasing frequency of drug name in a given drug class. In case of equal frequency regarding drug class (respectively drug name), alphabetical order will be used. In case any specific medication does not have ATC classification level 2 coded term, it will be summarized under “Unavailable ATC classification” category.

A listing of prior and concomitant medications will be created with the relevant information collected on the “Concomitant Medications Details” eCRF page.

All concurrent procedures, which were undertaken any time during the on-treatment period, will be summarized. A listing of concurrent procedures will be created with the relevant information collected on the “Concomitant Procedures Details” eCRF page.

